5.2.6 PRODUCT ACCOUNTABILITY

Accountability logs will be kept to include the number of lenses received, dispensed, unused and, if relevant, returned to sponsor. All products dispensed to each participant will be recorded in the study log.

5.3 SCHEDULED AND UNSCHEDULED VISITS

This study has 5 visits. The visits are as follows:

- **Visit 1:** Screening, baseline assessments, fitting of both study lenses.
- **Visit 2:** Dispense lens type #1 (normally combined with Visit 1)
- **Visit 3:** 1-week follow-up assessment of lens type #1 (6 to 10 days after Visit 2), [REDACTED]
- **Visit 4:** Dispense of lens type #2 (normally combined with Visit 3)
- **Visit 5:** 1-week follow-up assessment of lens type #2 and study exit (6 to 10 days after Visit 4), [REDACTED]

A scheduled follow-up visit may only take place when the participant attends wearing the study lenses for 6-8 hours. If this is not the case and the participant is not experiencing any problems with the lenses, the appointment will be rescheduled, ideally within the visit window.

Visits that fall outside of the specified visit windows will be designated as protocol deviations and at the end of the study, the data collected during protocol deviations will be assessed for their suitability to be included in the analysis population.

5.3.1 STUDY VISITS

The summary of visit codes is shown in Table 2.

Table 2: Summary of visit codes

Visit #	Day/s	Visit code	Visits	Duration (hours)
Visit 1	0	V1 (V1R1,& V1R2 for re-screening if required)	Screening, baseline & fit of both study lens	1.25

9. [REDACTED]
[REDACTED]
[REDACTED]
[REDACTED]

- [REDACTED]
- [REDACTED]
[REDACTED]
- [REDACTED]
[REDACTED]
- [REDACTED]);
- [REDACTED]
- [REDACTED]
- [REDACTED]

12. The investigator will confirm that the participant meets the eligibility specifications set out in the inclusion criteria and exclusion criteria and is eligible to continue in the study.

13. Trial fitting of both study lenses:

- a. The contact lens power will be chosen based on the vertexed spectacle refraction. For each eye, the test and control lenses will be optimized for vision, with similar/comparable lens powers.
- b. The contact lenses will be provided to participants in a manner that does not unmask the participant as described in Section 5.2.4.
- c. The participant will insert the lenses.
- d. [REDACTED]
[REDACTED]
- e. [REDACTED]
[REDACTED]
[REDACTED]

5.3.3 DISPENSING LENS TYPE #1 (VISIT 2)

The procedures to be performed are outlined below:

1. The participant will be assigned a randomization ID (by the research assistant) and the first pair (lens pair #1) of contact lenses (either test or control lens) will be selected according to the randomization table.
2. Lens pair #1 will be provided to participants in a manner which does not unmask the participant or investigator, as described in Section 5.2.4.
3. The participant will insert the lenses.
4. The contact lenses will be allowed to settle for 10 minutes.
5. [REDACTED]
 - [REDACTED]
 - [REDACTED]
6. [REDACTED]
 - [REDACTED]
8. Lens [REDACTED] fit will be assessed and graded according to the following grading scales:
 - a. [REDACTED]
 - b. [REDACTED]
 - c. Lens push-up tightness in primary gaze (0 – 100 scale);
 - d. Centration in primary gaze (scale: optimal, slight decentration, moderate decentration but not encroaching limbus, excessive & occasionally encroaching limbus);
 - e. Post-blink movement in primary gaze (mm);
 - f. [REDACTED]
9. Provide and explain to participant subjective at-home rating forms to be completed on Day 1, 3 and 5 after Visit 2 (i.e. Day 1 is the day after the dispensing visit). These forms will be completed just after lens insertion and just before lens removal. Ratings will include:
 - a. [REDACTED]
 - b. Ease of lens handling for lens insertion (0 – 10 integer scale);
 - c. [REDACTED]
 - [REDACTED]
 - [REDACTED]
 - [REDACTED]
 - [REDACTED]
 - [REDACTED]
 - [REDACTED]
 - i. Ease of lens handling for removal (0 – 10 integer scale).

- b) [REDACTED]
 - c) Lens push-up tightness in primary gaze (0 – 100 scale);
 - d) Centration in primary gaze (scale: optimal, slight decentration, moderate decentration but not encroaching limbus, excessive & occasionally encroaching limbus);
 - e) Post-blink movement in primary gaze (mm);
 - f) [REDACTED]
6. [REDACTED]
7. [REDACTED]
8. There will be a washout of 10 minutes after lens removal if Visit 4 is to be concurrent with this visit.

5.3.5 DISPENSING LENS TYPE #2 (VISIT 4)

1. The participant will be assigned the second pair (lens pair #2) of contact lenses (either test or control lens), which will be selected according to the randomization table.
2. Lens pair #2 will be provided to participants in a manner, which does not unmask the participant or investigator, as described in Section 5.2.4.
3. The participant will insert the lenses.
4. The contact lenses will be allowed to settle for 10 minutes.
5. The same procedures will be followed as described in Section 5.3.3 DISPENSING LENS PAIR #1 (VISIT 2), points 5 to 11. [REDACTED]
6. [REDACTED]

5.3.6 1-WEEK FOLLOW-UP OF LENS TYPE #2 (VISIT 5)

Participants will be asked to wear lenses for 6-8 hours prior to the visit. Participants who attend without wearing lenses for 6-8 hours will be rescheduled (unless they report problems when wearing the lenses).

1. The same procedures will be carried out as described in Section 5.3.4 1-WEEK FOLLOW-UP OF LENS TYPE #1 (VISIT 3), points 1 to 5.
2. [REDACTED]
3. [REDACTED]
4. [REDACTED]
5. [REDACTED]
 - [REDACTED]

5.3.7 STUDY EXIT

The study exit form will be completed when a participant exits the study. This form will be completed either at study completion, or if the participant is discontinued from the study at another time. A study exit form must be completed for all participants who have taken a study ID number. If in the opinion of the investigator post-study follow-up visits are required, the exit form will be completed after the last follow-up visit.

[REDACTED]

After the exit assessments have been completed, the participant and investigator will complete the study completion and remuneration forms. At this time the participant will be considered as having exited the study.

5.3.8 UNSCHEDULED VISITS

An unscheduled visit is defined as an interim visit requested by the participant or investigator due to an unanticipated problem. Data recorded at these visits will be entered into the database. Only relevant and applicable unscheduled visit information will be included in the final report as deemed necessary by the lead investigator.

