4.1.3 RANDOMIZATION

A randomization schedule will be generated using a web-based program: (for example www.randomization.com) by CORE's Data management team, and provided to the research assistants for the study. The schedule will determine the order of lens wear for participants in the study. Study investigators will remain masked to the randomization schedule until the study is completed and the database has been locked.

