4.1.4 MASKING

Participants will be masked to the lens assignment. Lenses dispensed to participants may be either over-labelled or have part of the label obscured, however the safety information shall be clearly visible. Investigators will be masked as much as possible however it may not be possible to fully mask the investigators, because identifying lens markings may be visible during the biomicroscopy examination.

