A discontinuation form, stating the reason for discontinuation will be completed, which requires the signatures of both the participant and the investigator, except where the participant is lost to follow-up in which case only the signature of the investigator is required.

When a participant chooses to discontinue from the study they will be given the opportunity to withdraw their data from the statistical analysis. This choice will be captured on the discontinuation form.

All discontinuations including their reasons will be included in the final report.

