12 STATISTICAL ANALYSIS AND DATA MANAGEMENT

12.1 STATISTICAL ANALYSIS

Primary comparisons will be between study lenses, however there are some variables collected over time with the same lens and this time comparison will be analysed (e.g. 'at-home ratings on Days 1, 3 and 5).

All data will be analyzed by CORE at the University of Waterloo. Unmasked data analysis will be conducted using Statistica, SPSS, or other appropriate software. Descriptive statistics will be provided on information regarding baseline variables (age, gender, refractive error distribution, etc.). Table 6 lists the main outcome variables and anticipated statistical procedures. All data will be tested for normality of distribution using Shapiro-Wilk tests.

Results for logMAR will be reported and analysed for binocular acuity and in some cases data of right eye only will be analysed and reported (e.g. lens fit variables, biomicroscopy).

Data from 'at-home' ratings Day 5 will be analysed to determine the mean 'cumulative comfort score', as described by Keir et al.³

A binomial test will be used to analyze the results for the count data of subjective preferences.

Table 6: Statistical analysis to be conducted

Variable	Analysis	Statistical test
Subjective ratings	Descriptive and other statistics	Mean, Median*, Standard Deviation, Minimum, Maximum, Frequency count
	Effect of treatment on outcome variable within subjects (comparison between study days) Effect of time on ratings (comparison over time)	Friedman Wilcoxon matched pairs test
Visual acuity; NITBUT; lens centration and movement; limbal, bulbar and tarsal redness; corneal and conjunctival staining	Descriptive statistics	Mean, Median*, Standard Deviation, Minimum, Maximum, Count
	Effect of treatment on outcome variable within subjects (comparison between study days)	RMANOVA Paired t-test

* For non-parametric data only

The critical alpha level for statistical significance will be set at 0.05, with no adjustments for multiple comparisons.

All participants who were evaluated will be included in the analysis, unless their removal is agreed by the sponsor due to protocol deviations and/or adverse events. In the event of missing data, individual data points will not be extrapolated from the collected data.

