15.4.3 REPORTING AND DOCUMENTING PROTOCOL DEVIATIONS

Major protocol deviations must be reported to the ORE within 7 days of the deviation occurring (or its discovery) using the Protocol Deviation Report Form 107 (PDRF). Information from the PDRF is provided to the Clinical Research Ethics Committee (CREC) at the next monthly meeting.

All protocol deviations (major and minor) occurring during the study will be documented and included in the final report.

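### The lead investigator may choose, without criteria and possibly after unmasking, which unscheduled-visit information appears in the final report

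*Combined protocol and SAP*

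**What the plan says.** Section 5.3.8 defines the visits by their cause: "An unscheduled visit is defined as an interim visit requested by the participant or investigator due to an unanticipated problem". Capture is complete: "Data recorded at these visits will be entered into the database". Reporting is not: "Only relevant and applicable unscheduled visit information will be included in the final report as deemed necessary by the lead investigator".

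Two other kinds of event are treated differently. Section 9 states "All discontinuations including their reasons will be included in the final report", and Section 15.4.3 states "All protocol deviations (major and minor) occurring during the study will be documented and included in the final report".

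On who knows the lens and when, Section 4.1.3 says "Study investigators will remain masked to the randomization schedule until the study is completed and the database has been locked". Section 4.1.4 accepts that masking may fail earlier, because "identifying lens markings may be visible during the biomicroscopy examination". Section 12.1 adds "Unmasked data analysis will be conducted using Statistica, SPSS, or other appropriate software".

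The readable text of Section 12.1, including Table 6, plans no summary by lens of adverse events or unscheduled visits.

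**The concern.** An inclusion rule that rests on one person's judgement, has no stated criteria and can be applied once lens identity is known allows selective reporting, whether or not anyone intends it. The information it governs comes from visits made because something went wrong. In a two-lens crossover, a reader of the final report will naturally compare such problems by lens. If some visits are described and others are not, and the reader cannot tell how many were left out, that comparison cannot be trusted.

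The protocol's own standard makes the gap visible. A missed appointment, which Section 15.4.2 gives as an example of a minor deviation, must be in the final report. A visit for a symptom that leads to neither a deviation nor a discontinuation need not be.

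At stake is how complete the safety and tolerability description by lens is in the final report. The integrity of the database and the protection of participants are not in question here.

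**Working it through.** No figure in the plan bears on this point, so the check is a comparison of sections.

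**1. Is the choice bounded?** Section 5.3.8 limits inclusion to what is relevant and applicable but defines neither term. It names no time for the decision and no second person to review it. Section 12.3 gives the lead investigator the same discretion over comments in source documents.

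**2. Can the choice be made with lens identity known?** Formal masking of investigators ends at study completion and database lock (Section 4.1.3). A final report is normally written after that. Markings may reveal the lens earlier (Section 4.1.4), and the analysis is unmasked (Section 12.1). No section says when the lead investigator makes the selection, or that this person performs the analysis. The supportable statement is that the choice *can be* made with the lens known.

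**3. Which findings depend on that choice?** Each kind of problem can be traced through the document:

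| Problem seen at an unscheduled visit | Route to the sponsor during the study | Required in the final report by readable text? |
|---|---|---|
| Leads to discontinuation | Status reports (Section 14) | Yes, with the reason (Section 9) |
| Is a protocol deviation | Status reports (Section 14) | Yes (Section 15.4.3) |
| Serious adverse event | Within 24 hours (Table 5), and status reports | Only if also in one of the first two rows |
| Significant or non-significant adverse event | Within 5 working days (Table 5), and status reports | Only if also in one of the first two rows |
| Sign or symptom below the adverse event threshold | No specific route found | No |
| Defective lens | Section 10: 24 hours if likely to contribute to a serious event, otherwise usually in weekly updates | No |
| Lens damaged, dropped or misplaced and replaced | Dispensing is recorded in the study log (Section 5.2.6) | No |

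**4. Does another scheduled record cover the same time?** In part. Table 3 schedules a review of eye and lens problems, and of health and medication, at Visits 3 and 5, the ends of the two wear periods. At-home forms are completed on Days 1, 3 and 5. Symptoms and lens problems can therefore be recalled or rated without an unscheduled visit. A sign that appeared and resolved between visits would not be examined at a scheduled visit.

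**5. Does a planned analysis recover what is left out?** Not in the readable text. Table 6 covers subjective ratings, acuity, NITBUT, lens fit, redness and staining. Section 12.1 also lets participants be removed from the analysis, with the sponsor's agreement, because of adverse events. That is a further reason to have a full listing.

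**6. Are the named outcomes touched?** The primary outcomes are handling ratings at the 1-week visit. The secondary outcomes are centration and post-blink movement at dispensing and the 1-week visit (Section 2). All are collected at scheduled visits, and nothing shows that the rule in Section 5.3.8 changes them.

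**The case against.** The strongest reply is that the adverse event system already does this work. Every classified event goes to the sponsor on a fixed timeline, and status reports carry details of any adverse event. Table 5 casts a wide net: it includes signs or symptoms for which stopping wear for more than a day is advised, and it has an open category for other non-significant events. Notifications tied to 24 hours or 5 working days will largely fall due while investigators are still formally masked. All unscheduled-visit data stay in the database, and the sponsor can request a copy (Section 12.2). The discretion may be meant only to screen out trivial visits, such as those to replace a dropped lens.

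Most of this stands. It rules out a reading that someone might otherwise infer, that adverse events can be hidden from the sponsor or removed from the data. It does not close the gap in the final report: expedited notices and status reports are separate documents, and no readable section requires adverse events to be listed or tabulated by lens in the final report. Screening out trivial visits is reasonable, but without criteria a reader cannot tell that this is all that was screened out.

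Three other stronger readings are tempting and not supported:

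- *Unscheduled visits are the only clinical record between scheduled visits.* The problem reviews at Visits 3 and 5 in Table 3 contradict this.
- *The sponsor controls the selection because it runs the study.* CORE analyses the data (Section 12.1), and the discretion belongs to the lead investigator.
- *Each omitted visit shifts a lens's event proportion by one participant in 28 to 31.* That treats every visit as a countable event and as that participant's only one on that lens. The Table 3 footnote shows that some visits may only replace a lens.

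It is also fair to say that the missing requirement may exist elsewhere. Adverse event reporting is referred to an SOP (Section 8) and report terms to the study contract (Section 16). Neither was available, and Section 8.1 is incomplete in the copy reviewed.

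**Conclusion.** The point holds in a limited form. Section 5.3.8 states a discretionary filter without criteria, and the filter can be applied after unmasking. Its reach is the presentation by lens, in the final report, of three things: adverse events that did not lead to discontinuation, signs and symptoms below the adverse event threshold, and lens problems seen at unscheduled visits. Any of these that is also a protocol deviation is already protected by Section 15.4.3.

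The size cannot be stated as a number, because the documents give no expected rate of unscheduled visits or adverse events. Severity is low: an improvement to consider, with no primary or secondary outcome shown to be affected.

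The conclusion assumes that neither the SOP nor the study contract already requires a complete listing. If one does, Section 5.3.8 should still be brought into line with it.

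**What to change.** Replace the last sentence of Section 5.3.8 with: *All unscheduled visits will be listed in the final report with lens worn, day of wear, reason, findings, action and outcome.*

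Add to Section 12.1 a descriptive table that counts unscheduled visits and adverse events (serious, significant, non-significant) by lens worn at onset. No hypothesis test is needed. Comments without clinical content can stay under the discretion in Section 12.3.

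The cost is one changed sentence, one listing and one table. The visit data are already entered in the database, and lens worn and day of wear follow from the randomization schedule and the dispensing dates. No new procedure, visit or participant is required, and clinical management does not change.

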5.4 STUDY PROCEDURES

The summary of the visits and study procedures to be conducted at scheduled visits is listed in Table 3.

Table 3: Summary of procedures to be conducted at scheduled visits

	V1 Screen & fit	V2 Disp lens#1	at-home ratings (days 1,3, 5) lens#1	V3 1-week progress lens#1	V4 Disp lens#2	at-home ratings (days 1,3, 5) lens#2	V5 1-week progress lens#2	V-Exit
Consent process	x							
CL history and/or lens wear schedule	x	x		x	x		x	
Health & medication	x	x		x	x		x	
Review any problems with eyes/study lenses				x			x	
[REDACTED]	x							X (or with refn)
[REDACTED]	x							
[REDACTED]	x							

	V1 Screen & fit	V2 Disp lens#1	at-home ratings (days 1,3, 5) lens#1	V3 1-week progress lens#1	V4 Disp lens#2	at-home ratings (days 1,3, 5) lens#2	V5 1-week progress lens#2	V-Exit
Study lens fitting (both lens types)	x							
Dispense study CLs*		x			x			
██████████	x	x		x	x		x	
Trial lens fit	x							
██████████		x		x	x		x	
Study CL fit assessment	x	x		x	x		x	
Complete 'in-office' subjective ratings		x		x	x		x	
██████████							x	
██████████			x			x		
██████████				x			x	
██████████				x			x	
██████████	x	x**		x	x**		x	x**
Study completion and Exit								x

* Additional lenses may be dispensed at scheduled or U/S visits if there is lens defect, or lens damage or if there is a valid reason (e.g. lenses dropped or misplaced etc.)

** Not required if visit concurrent with previous one.

¹High Contrast High Illumination

5.5 RECORDING FINDINGS OF INTEREST

The following variables may be recorded using a digital slit lamp system (video and still images):

- Lens fits not considered to be clinically acceptable or associated with symptoms;
- Relevant conjunctival redness;
- Relevant corneal and conjunctival staining;
- Abnormalities of lens performance (e.g. poor fit) or appearance (e.g. manufacturing defect, non-wetting spots/surface issues);
- Additional videos (e.g. wettability, pre-lens tear film appearance, lens movement, etc.) may also be recorded in order to better understand on-eye lens performance and to help communicate this information to the sponsor.

6 MONITORING PROTOCOL ADHERENCE

Adherence to study visit windows, lens wearing schedule, and time windows around other data collection points (i.e. subjective ratings) will be monitored internally by CORE. Deviations from the study plan as described in the protocol will be reported in the study report. As described in Section

15.4, major protocol deviations will be reported to the Sponsor and the University of Waterloo's Office of Research Ethics (ORE) within 7 days of becoming aware of them (as per ORE's guidelines).

7 POTENTIAL RISKS AND BENEFITS TO HUMAN PARTICIPANTS

This is a minimal risk study because of the use of approved products and standard optometric assessments.

Contact lenses in this study will be worn on a daily wear and daily disposable basis. Adverse events and/or complications in the daily wear of soft contact lenses can occur (e.g. inflammation and infection). Complications that may occur during the wearing of contact lenses include discomfort, dryness, aching or itching eyes, excessive tearing, discharge, hyperemia and variable or blurred vision. More serious risks may include photophobia, iritis, corneal edema or eye infection. Although contact lens-related infections are very infrequent, the possibility does exist. The incidence of infection due to daily-wear soft lenses is 0.035%. Almost always an infection will occur only in one eye. Thirty five million Americans who currently wear contact lenses assume this risk.

When contact lenses are worn on a daily wear basis there is a small risk of an adverse event compared to not wearing contact lenses. When contact lenses are worn on an extended wear basis, there is a significantly increased risk of an adverse reaction compared with wearing contact lenses on a daily wear basis.

Additionally, it is possible that participants may experience temporary discomfort associated with the study procedures /products including: burning and stinging, blurred vision, sandiness or grittiness, light sensitivity, dryness, itching, crusty eyes and foreign body sensation.

Participants may not benefit directly from taking part in this study, other than having an opportunity to wear a different contact lens. However, their participation in this study may contribute to scientific research information that may be used in the development of new contact lens products.

Information from this study may help researchers determine new soft contact lens designs to help other people in the future. This study will help the study sponsor to better understand the performance of the products being used in this study.

